5. BACKGROUND INFORMATION

5.1 Background

Allogeneic blood and marrow transplantation (HSCT) are increasingly employed in the treatment of hematological and oncological malignancies and are now standard procedures for selected diseases. During, immunosuppressive treatment is required to reduce the risk of transplant rejection and graft-versus-host disease (GVHD).

Serious infections are common in the early phase following allogeneic HSCT because immune reactivity during the first month post-transplant is very low. Effective approaches toward vaccinating patients against common pathogens are being explored but are limited by poor levels of responsiveness. Protective immunity to diseases preventable by routine vaccination is lost following allogeneic HSCT. Adoptive transfer of immunity from donors to recipients after allogeneic transplantation is not sufficient to prevent this decline. However, vaccination practices after transplantation vary and data are sparse [1, 2].

Following transplantation, cytotoxic and phagocytic functions recover by day 100, but the more specialized function of T and B lymphocytes may remain impaired for a year or even longer. Deficiencies in cellular immunity are characterized by the inversion of CD4/CD8 ratios, a decreased proliferative response to mitogens, and the development of anergy to recall antigens as measured by delayed-type hypersensitivity testing. The impact on humoral immunity consists of decreased levels of circulating immunoglobulins, impaired immunoglobulin class switching, and a loss of complexity in immunoglobulin gene rearrangement patterns. The efficacy of vaccination following HSCT is influenced by the time elapsed since transplantation, the nature of the hematopoietic graft, the use of serial immunization, the vaccine being used, and the immune status of the patient including the presence of chronic GVHD [3]. After one to three years after allogeneic HSCT patients without chronic GVHD experience complete immune regeneration whereas in patients with chronic GVHD immunodeficiency can remain for prolonged periods of time [4-6].

Chronic GVHD continues to be a major problem in long-term survivors of allogeneic HSCT, affecting 35-70% of patients [7, 8]. The pathogenesis and clinical features of chronic GVHD resemble those of several autoimmune diseases such as systemic lupus erythematosus, Sjogren's syndrome and scleroderma. Autoreactive T lymphocytes are an important effector mechanism with interferon gamma playing a central role in the increased collagen deposition that is a central histopathologic feature of chronic GVHD [9]. Since chronic GVHD only occurs in allogeneic HSCT recipients and can be prevented by T-cell depletion from the donor graft, donor T-cells responding to allogeneic antigens in the patient are of critical

importance for the development of chronic GVHD. Of note, donor B-cell responses to recipient HY antigens have been significantly associated with the development of chronic GVHD in the setting of gender mismatched HSCT.

Chronic GVHD can affect the skin (depigmentation, poikiloderma, lichen planus-like features, sclerotic features, morphea-like features, lichen sclerosus-like features lichenoid papules), the liver (hepatitis), the lung (obliterative bronchiolitis), the oral mucosa (lichen-type features, hyperkeratotic plaques, restriction of mouth opening from sclerosis, ulcerations, atrophy of the mucosa, xerostomy), eyes (keratoconjunctivitis sicca), muscles and fibers (myositis, tendinitis, and fasciitis), and the esophagus (esophageal web, strictures or stenosis), respectively. The diagnosis of chronic GVHD requires the presence of at least one diagnostic clinical sign of chronic GVHD (e.g. poikiloderma) or the presence of at least one distinctive manifestation (e.g. keratoconjunctivitis sicca) confirmed by pertinent biopsy or other relevant tests (e.g. Schirmer test) in the same or another organ. According to the consensus of the National Institute of Health (NIH) in 2005 a new clinical scoring system (0-3) was introduced to assess the extent and severity of chronic GVHD for each organ or site at any given time, with 0 representing no involvement and 3 reflecting severe impairment [10]. For mild forms, no treatment is necessary. Extended disease requires specific immunosuppressive treatment using corticosteroids +/- cyclosporine, tacrolimus, and monoclonal antibodies such as basiliximab or tumor necrosis factor-alpha inhibitor as etanercept [11]. These immunosuppressive regimens may additionally impair patients' response to vaccination. Therefore, infections have become increasingly important during GVHD therapy [12]. Immunosuppressive therapy is being improved continually and in most cases little is known about the impact of the more recently adopted regimens on durability of antibody response. Thus, studies on immune-response after vaccination in patients with different immunosuppressive regimes are still missing.

Tick-borne encephalitis (TBE) is a disease of the central nervous system caused by a tickborne flavivirus infection. TBE can lead to severe neurological symptoms such as meningitis, meningoencephalitis, and meningoencephalomyelitis, which can result in death. There is no treatment, and prevention with the vaccine is the only intervention currently available. TBE is the most important arthropod-transmitted viral disease in Europe, and in some countries it represents a major public-health problem [13]. In Austria and the southern parts of Germany TBE is endemic and therefore it is assumed that the whole population living in those areas is at risk. In the pre-vaccination era, Austria had the highest recorded morbidity of TBE in Europe. The disease accounted for more than 50% of all viral meningoencephalitides in the eastern and southern parts of the country [14]. Flaviviruses are a large group of small, enveloped viruses responsible for a number of severe human diseases, including yellow

fever, Japanese encephalitis, dengue hemorrhagic fever and TBE. TBE virus particles are roughly spherical in shape, 40-50nm in diameter, and contain a core, 20-30nm in diameter. The genome consists of single-stranded positive-sense RNA with a relative molecular mass of about $4x10^6$. Three structural proteins and the capsid, membrane and envelope proteins are all encoded by the viral genome. The envelope glycoprotein induces neutralizing and hemagglutination-inhibition antibodies and is the most important antigen for providing protection from disease.

The first vaccine against TBE was prepared in 1941 in the brains of mice. Some 20 years later TBE vaccines derived from cell cultures (chicken embryo fibroblast cells) were developed and used for active immunization in humans in the former Soviet Union. Later, a purified, inactivated virus vaccine was developed which proved to be more immunogenic than previous TBE vaccines. The efficacy of these vaccines has been well documented. All the currently licensed TBE vaccines (Encepur children, Encepur Adults, and FSME-IMMUN "new") gave high seroconversion rates of over 87% in immunocompetent individuals. Although systemic and local adverse event were commonly reported, none were serious or life-threatening [15].

Following allogeneic HSCT, TBE vaccination should be performed as primary immunization in risk area with three vaccine-doses after the first nine to twelve months (CIII recommendation) [16].

Adequacy of the immune response to a vaccine is frequently measured by the serum level of the specific antibody. Although seroconversion does indicate an immune response, it does not necessarily signify protection. While routine determination of antibody titers prior to vaccination is not recommended in all transplant recipients, post-vaccination determination of antibody levels is useful to monitor antibody response and protection, and assess the need for additional doses of the vaccine [1]. Successful vaccination can be easily monitored by the demonstration of specific immunoglobulin G-antibodies in the serum by enzyme-linked immunosorbent assay (ELISA). However, there is a potential for misleading results, because all flaviviruses are serologically related and infections or vaccinations with one flavivirus will give rise to antibodies that also react with all other flaviviruses in ELISAs. Vaccinations against yellow fever, Japanese encephalitis or infections with dengue viruses will thus result in cross-reactive but non-neutralizing antibodies yielding a positive result in TBE ELISAs [13]. Detectable neutralizing antibodies are generally viewed as a surrogate parameter of protection against TBE infection because their formation is of decisive importance for virus elimination and entails protection against the disease [17].

Serological response to TBE vaccination has already been studied in different populations with decreased responsiveness to vaccines, the HIV-positive patients [18], in the elderly [19, 20], and in heart transplant recipients [21], respectively.

For pneumococcal polysaccharide vaccine, lack of responsiveness to vaccination in HSCT patients with chronic GVHD has been demonstrated [22]. But there is little information on the efficacy of the TBE vaccine in stem cell transplant recipients with chronic GVHD.

5.2 Study rationale

Patients undergoing HSCT experience a prolonged period of dysfunctional immunity associated with an increased risk of bacterial and viral infections. Systematic reimmunization is necessary at appropriate time intervals following transplantation to reestablish immunity [1]. TBE vaccination should be performed as primary immunization in risk area with three vaccine-doses nine to twelve months after allogeneic HSCT (CIII recommendation) [16]. However, immune response after vaccination might vary a lot among HSCT patients with and without chronic GVHD. In a study with immunosuppressed heart transplant recipients a seroconversion rate of 35% was detected compared to 100% in the healthy control group [21]. Similarly, we assume that the serum conversion rate after TBE reimmunization is significantly reduced in HSCT recipients compared to an age-matched and sex-matched control group of healthy volunteers without previous TBE vaccination. Moreover, it is not clear whether TBE vaccination in HSCT patients with chronic GVHD has a protective effect at all.

The results of the planned pilot study will provide first data to assess the efficacy of TBE vaccination in allogeneic HSCT recipients with and without chronic GVHD. These data will enable to develop new guidelines or optimize current guidelines for TBE vaccination in this special population at risk. It is expected that different guidelines for HSCT patients with and without chronic GVHD have to be established in the future.

6. STUDY OBJECTIVES

The aims of this study are to estimate the humoral and cellular immune responses after TBE vaccination in adult HSCT recipients.

6.1 Primary Objective (Hypothesis)

To assess the humoral immunogenicity to a TBE vaccination in allogeneic HSCT recipients compared to healthy volunteers without previous TBE vaccination, the quantitative antibody

levels will be measured using neutralilzation test (NT) and enzyme-linked immunosorbent assay test (ELISA).

The null hypothesis has to be rejected that there is no difference in the seroconversion rate between the HSCT patients and the healthy volunteers after TBE vaccination.

6.2 Secondary Objectives

To assess cellular immunogenicity of the TBE vaccination in allogeneic HSCT recipients, Tcell cytokine expression will be measured using flow-cytometry after in vitro stimulation with peripheral blood mononuclear cells with TBE antigen.

To evaluate the immune status in HSCT recipients prior to and after vaccination, quantitative immunoglobulin levels will be measured and immunofluorescence staining of peripheral blood T and B lymphocytes and flow cytometry analyses will be performed.

7. STUDY DESIGN

A prospective open-label phase II pilot study will be performed. A total of 52 adult male or female subjects, 26 HSCT patients (study population) and 26 healthy volunteers (control group), will be enrolled in this clinical trial. Eight study visits per patient will be planed. Eligible patients will receive at least two TBE vaccinations (study visit 1 – day 0, study visit 2 -1month after the first vaccination) with a total of two doses of the TBE vaccine FSME IMMUN®. Whenever possible, the patients will receive complete primary vaccination with a third dose of TBE vaccine FSME IMMUN® (study visit 9 - 12 months after the first vaccine will be injected intramuscularly in the Musculus deltoideus.

FSME IMMUN® contains formalin-inactivated TBE virus. One dose (0.5 ml) contains 2.4 µg of antigen inactivated by formaldehyde. Human albumin is used as stabilizer and aluminium hydroxide is used as adjuvant. The vaccine contains traces of formaldehyde, protamine sulphate, neomycin and gentamicin.

Serum samples for determination of antibody levels will be obtained immediately before the first (study visit 1), 4 weeks after the second vaccination (study visit 4), and four weeks after the third vaccination (study visit 8). Blood samples for the analysis of cellular immunity will be taken before the first (study visit 1), one week after the second vaccination (study visit 3) and one week after the third vaccination (study visit 7). Blood samples for determination of the immune reconstitution and the quantitative immunoglobulin levels will be obtained prior to the first (study visit 1) and third vaccination (study visit 6) and 12 weeks after the first vaccination (study visit 5) in HSCT recipients only.

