7.1.5 Withdrawal and replacement of subjects

Criteria for withdrawal

Subjects may prematurely discontinue from the study at any time. Premature discontinuation from the study is to be understood when the subject did not undergo complete the last visit (study visit 8) and / or all pivotal assessments during the study.

Subjects must be withdrawn under the following circumstances:

- at their own request
- if the investigator feels it would not be in the best interest of the subject to continue
- if the subject violates conditions laid out in the consent form / information sheet or disregards instructions by the study personal

In all cases, the reason why subjects are withdrawn must be recorded in detail in the CRF and in the subject's medical records. Should the study be discontinued prematurely, all study materials (complete, partially completed and empty CRFs) will be retained.

Follow-up of patients withdrawn from the study

In case of premature discontinuation after start of vaccination, no further investigations concerning the study will be performed. Furthermore, participants may request that from the time point of withdrawal no more data will be recorded and that all biological samples collected in the course of the study will be destroyed.

Replacement policy

If the week 8 (primary endpoint) is reached, drop-outs will be included in the sample size. If the participiant drops out before the week 8 is reached, patients will be replaced and the next free subject number will be allocated.

7.1.6 **Premature termination of the study**

The sponsor has the right to close this study at any time. The IEC and the competent regulatory authority must be informed within 15 days of early termination.

The trial or single dose steps will be terminated prematurely in the following cases:

- If adverse events occur which are so serious that the risk-benefit ratio is not acceptable.
- If the number of dropouts is so high that proper completion of the trial cannot realistically be expected.

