8.1.1 Dosage and administration

Initial dose: All subjects will receive one dose 0.5 ml TBE vaccine FSME IMMUN on day 0 (study visit 1).

Repeated dose: All subjects will receive one additional dose 0.5 ml TBE vaccine FSME

IMMUN on week 4 (study visit 2) and between week 40-52 (study visit 6).

Route of administration: TBE vaccine will be injected intramuscularly in the Musculus deltoideus.

Duration: All subjects will receive 0.5 ml TBE vaccine three times within one year.

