8.5.2.7. Visit 6 /3. Vaccination and evaluation of immune status (Day 270-365)

The following activities will be performed:

- The investigator will ask all subjects about any adverse experiences occurring since Visit 5. All adverse experiences will be documented in the CRF.
- Physical examination including body temperature measured axillary.
- Pregnancy test in females capable of bearing children.
- Third vaccination: for details see Visit 1.
- Post vaccination observation period (30 minutes): for details see Visit 1.
- Blood draw of 10 ml for immune status and quantitative immunoglobulin levels

8.5.2.8. Visit 7 /2. Evaluation of cellular immunity (Day 277-372, 7 ± 2 days after the third vaccination)

The following activities will be performed in HSCT patients only:

- The investigator will ask all subjects about any adverse experiences occurring since Visit 6. All adverse experiences will be documented in the CRF.
- Blood draw of 40 ml for cellular immunity

8.5.2.9. Visit 8 /2. Evaluation of humoral immunity (Day 298-393, 28 ± 7 days after the third vaccination)

The following activities will be performed in HSCT patients only:

- The investigator will ask all subjects about any adverse experiences occurring since Visit 7. All adverse experiences will be documented in the CRF.
- Blood draw of 10 ml for serum antibody determination (NT, ELISA)
- Pregnancy test in females capable of bearing children.

After this visit, the patients will have completed the study.

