11.1 Sample size considerations

For our phase II pilot study a calculation of the sample size was performed using nQuery 6.1. The primary endpoint is the outcome of the NT against 4 weeks after the second vaccination (positive test: Yes/No). Because of deviation of the antibody concentrations from normal distribution (NT level <=10 not detectable indicating a negative test), the outcome is reduced to a binary but clinically more relevant outcome (seroconversion rate: NT levels >10 indicates a positive test). Previously, in a study with heart transplant recipients a seroconversion rate of 35% was detected compared to 100% in the healthy control group [21]. In our study we expect a seroconversion nate of at least 90% in the healthy control group. In the HSCT patients we expect a seroconversion not exceeding 50%. The calculation of the sample size was performed using the following assumption: Significance level alpha 0.05, Power 0.8, ratio of HSCT patients/healthy volunteers: 1/1. With a total number of 46 participants (23 HSCT patients and 23 healthy volunteers) the assumed difference in the seroconversion rate between groups can be detected (using a two-sided Fisher's Exact Test) with 80% Power. We added 10% to adjust for potential loss-to-follow-up which results in 26 HSCT patients and 26 healthy volunteers.

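### The third dose is conditional in section 7 and given to everyone in section 8.1.1, so the descriptive post-dose-3 rate, and its comparison with the post-dose-2 rate, can reflect who was sampled rather than the dose

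*Combined protocol and SAP*

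**What the plan says.** Three parts of the protocol treat the third dose differently.

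- **Section 7 (Study design)** promises at least two vaccinations and makes the third conditional: "Whenever possible, the patients will receive complete primary vaccination with a third dose".
- **Section 8.1.1 (Dosage and administration)** has no such condition: "All subjects will receive 0.5 ml TBE vaccine three times within one year".
- **Section 7.1.5 (Withdrawal and replacement)** ties completion to visit 8: "Premature discontinuation from the study is to be understood when the subject did not undergo complete the last visit (study visit 8"), and/or all pivotal assessments, a term it does not define. Table 1 and section 8.5.2.9 time visit 8 from the third vaccination.

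The windows also differ. Section 8.1.1 gives weeks 40-52. Table 1 and section 8.5.2.7 give days 270-365.

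The synopsis lists the antibody response after the second and third vaccinations under efficacy endpoints. Section 8.5.4.2 makes NT after dose 3, compared with NT after dose 2, a secondary endpoint, and section 11.3 analyses secondary endpoints descriptively. Sections 11.3 and 11.4 include eligible subjects who have results and do not impute.

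**The concern.** A subject who stops after two doses follows section 7, departs from section 8.1.1 and is a premature discontinuation under section 7.1.5. A site cannot tell from the text how to record that subject, and two sites of information in the report (deviations and discontinuations) could treat the same subject differently.

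The statistical consequence concerns the post-dose-3 results. By the visit schedule, dose 3 falls at least 270 − 56 = 214 days after the nominal day of the primary sample. If receiving it depends on what is feasible for the patient, the subjects sampled at visit 8 may differ from those sampled at visit 4. Sections 5.1 and 5.2 say that vaccine response varies with immune status and chronic GVHD, so a link between receiving dose 3 and responding is plausible, though the documents do not establish one. Section 8.5.4.2 then compares the two time points without saying that the same subjects must contribute to both. A rise from dose 2 to dose 3 could come partly from who dropped out of the denominator. Section 5.2 intends the data to inform vaccination guidelines, so the distinction matters to the reader of the results.

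**Working it through.** **1. The plan's own figure.** Inputs from section 11.1: "Significance level alpha 0.05, Power 0.8, ratio of HSCT patients/healthy volunteers: 1/1"; a rate of "at least 90% in the healthy control group"; at most 50% in HSCT patients; two-sided Fisher's exact test. Full enumeration of the exact power at 90% versus 50% gives 0.786 with 22 per group and 0.811 with 23. The stated 23 per group reproduces. Adding 10% gives 23 × 1.10 = 25.3, rounded up to 26, as stated. All of this concerns the sample after dose 2, so the third-dose question does not touch it.

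**2. The windows.** Weeks 40-52 are days 40 × 7 = 280 to 52 × 7 = 364. The visit schedule allows days 270-365, which is 96 days. Days 270-279 (10 days) and day 365 (1 day) lie inside the schedule and outside section 8.1.1: 11 of 96 days.

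**3. How far the available-case rate can move.** Let p be the rate if every two-dose subject had received dose 3 and been sampled, m the proportion without dose 3, and r the rate those subjects would have had. The reported rate is (p − m·r)/(1 − m). The documents give none of these three values. Assume p = 70% and m = 10% or 20%, and let r vary:

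| r among those missing | m = 10% | m = 20% |
|---|---|---|
| 0% (all non-responders) | 0.70/0.90 = 78% | 0.70/0.80 = 88% |
| 50% | (0.70 − 0.05)/0.90 = 72% | (0.70 − 0.10)/0.80 = 75% |
| 70% (unrelated to response) | (0.70 − 0.07)/0.90 = 70% | (0.70 − 0.14)/0.80 = 70% |
| 100% (all responders) | (0.70 − 0.10)/0.90 = 67% | (0.70 − 0.20)/0.80 = 62.5% |

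The last row shows that the direction, too, depends on r.

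**4. Composition mistaken for effect.** Take 26 HSCT patients at the planning rate after dose 2: 13/26 = 50%. Suppose 5 of the non-responders get no third dose, dose 3 converts nobody, and the 13 stay positive (assumptions). The available-case rate after dose 3 is 13/21 = 62%, an apparent gain of 12 percentage points. In the 21 patients with both samples, the rate is 13/21 at each time point, so the paired comparison shows no change. Over all 26 it stays at 13/26.

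**5. Gap between available-case rate and lower bound.** With about 70% positive among those sampled, 3 of 26 missing gives 16/23 = 70% against 16/26 = 62%. With 6 missing it is 14/20 = 70% against 14/26 = 54%.

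Steps 4 and 5 use the HSCT group. Section 8.5.2.9 restricts visit 8 to HSCT patients while Table 1 shows no such limit. That is a separate discrepancy, and nothing here relies on it.

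**The case against.** The case against is strong on several counts, and most of it stands.

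- A reader might infer that the post-dose-3 endpoints have no denominator. Sections 11.3 and 11.4 define one: eligible subjects with results, no imputation. What can be criticised is that this set may be selected.
- A reader might infer that two-dose subjects are lost to the trial. Section 7.1.5 keeps drop-outs in the sample size once week 8 is reached and replaces only earlier ones. The label removes nobody from the primary analysis.
- A reader might infer that the label could trigger early termination. Section 7.1.6 gives no count or threshold, so the documents do not support that step.
- The window gap is small, and section 8.5.1 makes the flow-chart margins admissible. It is a matter of consistency, with no shown effect on an endpoint.
- A reader might take 78-88% as the expected bias. It is the extreme in which every missing patient would have failed. The 10-20% missing is assumed, and sections 7.1.5 and 8.1.3 also allow for subject request and administrative reasons, which need not be related to response.
- The information is largely collected: reasons for withdrawal and for stopping vaccine go in the CRF (7.1.5, 8.1.3), and deviations are listed in the report (11.2).
- Counting subjects without dose 3 as non-responders answers a different question from response to the third dose, and would label some dose-2 responders as failures.

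What the objection does not remove is the direct conflict between sections 7 and 8.1.1, the overlap with the discontinuation definition, and the absence of any planned table or paired set that would let a reader separate composition from effect.

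**Conclusion.** The point holds in a limited form. The protocol contradicts itself on whether the third dose is required, and a subject treated as section 7 permits meets the section 7.1.5 definition of premature discontinuation. The difference in windows is real but minor.

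The primary comparison is sound on this point. The weakness is confined to a secondary, descriptive result: the post-dose-3 seroconversion rate and its comparison with the post-dose-2 rate depend on who received dose 3 and was sampled. Its size cannot be determined from the documents. Under an assumed true rate of 70% and 10-20% without dose 3, the distortion runs from none to a reported 78-88% at the unfavourable extreme, with 72-75% if half of those missing would have responded. It would reverse if those missing responded better than average. The change is worth making because it costs little and the post-dose-3 response is a named efficacy endpoint.

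**What to change.** Reconcile section 7, section 8.1.1, section 7.1.5, Table 1 and section 8.5.2.7 on three matters: whether the third dose is required, its window, and whether a two-dose subject is a premature discontinuation. No schedule is proposed here.

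In section 11.3, keep the available-case rate after dose 3 and add:

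- (a) the number of subjects without a third dose, with reasons and their NT result after dose 2;
- (b) the dose-3 versus dose-2 comparison in the paired set, meaning subjects with both samples;
- (c) a sensitivity analysis, labelled as a lower bound, giving the post-dose-3 rate over all two-dose subjects with those lacking a dose-3 result counted as non-responders.

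The cost is protocol wording and one extra descriptive table, built from data the CRF already collects. The sponsor should accept that the lower-bound rate may look less favourable than the available-case rate.
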